12.1.1 Primary Safety Analysis

AEs with grade 3 intensity or greater are classified as severe AEs. The frequency distribution of participants who experienced 1, 2, or ≥ 3 severe AEs occurring from Day 1 through Day 15 will be summarized by treatment group. The frequency and proportion (expressed in percent) of participants and 95% CI for proportions in each category will be provided. For computing proportions, the denominator is the number of participants in the Safety population for the given treatment group.

Serious AEs will be summarized similarly as described for severe AEs.

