1.1.9.2. Safety

The frequency of patients who experience one or more severe and/or serious SAEs will be summarized by treatment group with 95% CIs. The proportion of patients with this endpoint within each of the TBA-7371 treatment groups will not be formally compared to the control arm given limitations due to small sample sizes. The primary safety analysis will be performed in the Safety population.

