9.4. Statistical Analyses

A detailed statistical analysis plan (SAP) centered on primary and secondary endpoints will be developed and finalized prior to initiation of enrollment and will further describe the participant populations to be included in each analysis, details of the statistical methods, including procedures for accounting for missing, unused, and spurious data. Primary and secondary analyses are summarized in Table 9.

Exploratory endpoint analyses will be described in a separate exploratory scientific SAP(s) (exploratory SSAP). Specific objectives and hypotheses related to exploratory biomarker analyses will be documented in this exploratory SSAP prior to full data unmasking and analysis.

Results from the exploratory analyses may be reported in a separate results memo and included as an addendum to the clinical study report (CSR).

Table 9. Summary of Primary and Secondary Endpoints and Analyses

Endpoint	Statistical Analysis
Primary Bactericidal Effect	
Slope i.e. average change per day from screening (“0”) to Day 14 [$BA_{CFU}(0-14)$] of the log CFU counts.	For each patient, linear and bilinear regression models will be fit, and the better fit model based on lower AIC will be used to estimate [$BA_{CFU}(0-14)$] of log CFU counts from screening to Day 14. The log CFU screening measurement used in the model will be the average of the two individual screening measurements. An ANCOVA model will be used to quantify the evidence that each of the treatment group mean $BA_{CFU}(0-14)$ is less than 0 (i.e., that the treatment group mean has a negative slope on average). Multiplicity will be handled by means of a step-down sequential approach. The study will be declared a success if at least one of the TBA-7371 treatment groups achieves a statistically significant 1-sided p-value and demonstrates an acceptable safety profile.
Primary Safety	
Frequency of study participants who experienced one or more severe AEs and/or SAEs	The frequency of patients who experienced one or more severe and/or serious AE will be summarized by treatment group.
Secondary Bactericidal Effect	

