9.4.2. Safety Analyses

9.4.2.1. Primary Safety Analyses

The frequency of patients who experienced one or more severe AEs and/or SAEs will be summarized by treatment group with 95% CIs. The proportion of patients with this endpoint within each of the TBA-7371 treatment groups will not be formally compared to the control arm given limitations due to small sample sizes. The primary safety analysis will be performed in the Safety population.

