5 OBJECTIVES AND ENDPOINTS

5.1 Primary Objectives and Endpoints

The primary bactericidal activity objective of this study is to demonstrate the 14-day early bactericidal activity from screening (“0”) to day 14 (EBA 0-14) of 5 dose regimens of TBA-7371 monotherapy and Isoniazid[H], Rifampicin[R], Pyrazinamide[Z], Ethambutol[E] (HRZE) fixed dose combination, as assessed by colony forming unit (CFU) counts on solid media culture. The primary endpoint associated with this objective is the average change per day, from screening (“0”) to day 14 [BAcfu(0-14)] of the \log_{10} CFU/mL counts.

The primary safety objective of this study is to assess the severe/serious adverse event (AE) burden of 5 dose regimens of TBA-7371 monotherapy and HRZE over a 14-day treatment period. The primary endpoint associated with this objective is frequency of study participants who experienced one or more severe (\geq grade 3) and /or serious AEs from day 1 to through day 15.

Primary early bactericidal activity and safety objectives and associated endpoints are summarized in the [Table 1](#).

Table 1. Primary Objectives and Endpoint

Objectives	Endpoint
Early bactericidal activity	
Demonstrate the 14-day EBA from screening (“0”) to day 14 of 5 dose regimens of TBA-7371 monotherapy and HRZE as assessed by CFU counts on solid media culture.	Slope, i.e. average change per day, from screening (“0”) to day 14 [BAcfu(0-14)] of the \log_{10} CFU/mL counts.
Safety	
Assess the severe/serious AE burden of 5 dose regimens of TBA-7371 monotherapy and HRZE over a 14-day treatment period.	Frequency of study participants who experienced one or more severe (\geq grade 3) and /or serious AEs from Day 1 through Day 15.

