6.4 Safety Measures

Table 4. Safety Endpoint

	Endpoint
Primary safety	Frequency of study participants who experienced one or more severe (\geq grade 3) and/or serious AEs from Day 1 through Day 15.
Secondary safety	
Adverse events from Day 1 through Day 15:
 
 • Frequency from Day 1 through Day 15 of participants with AEs and frequency of AEs: overall, by system organ class and preferred term; by seriousness, severity, expectedness and relatedness to study drug. 
Eye symptoms from Day 1 through Day 15:

Table 4. Safety Endpoint

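### SAP 12.1.1 does not specify the primary safety estimate (participants with at least one severe and/or serious AE, with its 95% CI) that the protocol and the SAP's own endpoint sections define

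*SAP*

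**What the plan says.** **Endpoint and required analysis.**
- Protocol 9.4.2.1: "The frequency of patients who experienced one or more severe AEs and/or SAEs will be summarized by treatment group with 95% CIs". The synopsis (protocol 1.1.9.2) also asks that this "will be summarized by treatment group with 95% CIs".
- Protocol Table 9 states the same composite: "The frequency of patients who experienced one or more severe and/or serious AE will be summarized by treatment group".
- The SAP carries the composite forward in 5.1 ("The primary endpoint associated with this objective is frequency of study participants who experienced one or more severe") and in 6.4, Table 4 ("Frequency of study participants who experienced one or more severe"). Both entries go on to include serious AEs and the Day 1 to Day 15 window.

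**Analysis specified in SAP 12.1.1.**
- For severe AEs: "The frequency distribution of participants who experienced 1, 2, or ≥ 3 severe AEs occurring from Day 1 through Day 15".
- For intervals: "The frequency and proportion (expressed in percent) of participants and 95% CI for proportions in each category will be provided".
- For serious AEs: "Serious AEs will be summarized similarly as described for severe AEs".

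**Related text.** The overview table in SAP 12.1.2.1 has separate lines for highest intensity Grade 3 or above and for serious AEs, with no CI. SAP 12.1 plans by-participant AE listings. SAP 8 declares no change from the protocol's planned analyses. SAP Appendix 4 gives code for a mid-P 95% CI for a single proportion.

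**Laboratory days (separate point).** Protocol 8.3.4 schedules post-baseline safety samples on Days 3, 7, 15 and 42, and protocol Table 4 limits on-treatment samples to Days 3 and 7. The summaries and shift tables name Days 3, 7, 14 and 42. SAP 9.8 uses nominal visits and applies no windows.

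**The concern.** Severe and serious are different classifications; protocol 10.2.6.3 makes the distinction explicitly. A participant may be in either class or in both, so the composite is a union of two sets. SAP 12.1.1 tabulates each set separately and splits it by number of events. It contains no row for the union. Its CIs attach to the count categories, not to the proportion of participants with at least one event.

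A programmer who follows the section headed as the primary safety analysis would therefore produce two component distributions and not the primary estimate. What is at stake is whether the report contains the single descriptive figure, with its interval, that the protocol names as primary for safety.

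The laboratory point is smaller: the end-of-treatment sample has no summary column bearing its own scheduled day.

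**Working it through.** **The plan's own safety figures.** The plan's only safety calculations are detection probabilities, 1 − (1 − p)^n.
- n = 15: p = 10% gives 79.4% (stated as about 80%), p = 15% gives 91.3% (about 90%), p = 5% gives 53.7% (54%).
- n = 75: p = 3% gives 89.8% (90%).

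They reproduce. The point does not depend on them.

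**Is the composite planned anywhere?**

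| Place | Composite of severe and/or serious | 95% CI for the composite |
|---|---|---|
| Protocol 9.4.2.1 and 1.1.9.2 | yes | yes |
| Protocol Table 9 | yes | not stated |
| SAP 5.1 and 6.4 (endpoint definition) | yes | not stated |
| SAP 12.1.1 (analysis) | no: severe and serious apart, each split 1, 2, ≥3 | no: one CI per category |
| SAP 12.1.2.1 (overview) | no: separate lines | no |

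**What the two 12.1.1 tables determine.** Let s be the number with any severe AE, r the number with any serious AE, and k the number with both. Adding the 1, 2 and ≥3 rows gives s, and likewise r. The composite is s + r − k, with k anywhere from 0 to the smaller of s and r. Neither table shows k.

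**Illustration.** The documents give no expected severe or serious AE rates, so these counts are assumed. Group size is 15, and intervals are mid-P 95%.

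| s, r | k | Composite | % (95% CI) |
|---|---|---|---|
| 3, 2 | 2 | 3 + 2 − 2 = 3/15 | 20.0 (5.4 to 45.3) |
| 3, 2 | 1 | 3 + 2 − 1 = 4/15 | 26.7 (9.1 to 52.5) |
| 3, 2 | 0 | 3 + 2 − 0 = 5/15 | 33.3 (13.4 to 59.2) |

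**Do the category CIs help?** Take three participants with severe AEs, one in each count category. SAP 12.1.1 would print three rows of 1/15 (6.7%, 0.3 to 28.7). The estimate for at least one severe AE is 3/15 (20.0%, 5.4 to 45.3). The count follows by addition; the interval does not.

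**Laboratory days.** Sampled: 3, 7, 15, 42. Summarised: 3, 7, 14, 42. Three of the four post-baseline days match. Day 14 is named in seven places: protocol Tables 2, 6 and 9 and section 9.4.2.2; SAP Tables 2 and 4 and section 12.7.

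**The case against.** The strongest reply is that nothing is lost. The SAP defines the composite correctly in two places and declares no change, so a careful programmer would derive it. The 12.1.2.1 overview already gives the number with at least one severe AE and the number with at least one serious AE. Its rows for any AE and for highest intensity Grade 1 and Grade 2 can also narrow the overlap: if every participant with an AE has one of Grade 3 or higher, the composite equals the severe count. With 15 per group, the composite count can be read from the AE and SAE listings. The wide ranges above also need serious events that are not severe. The DAIDS grading text in protocol Appendix 4 puts events for which hospitalisation is indicated at Grade 3, so many serious events would be severe too.

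All of this stands. It rules out the stronger reading that the composite is unrecoverable, or that all planned output would be blind to the overlap. It does not supply the missing item. The section that specifies the primary safety analysis has no composite row, and no planned table gives its 95% CI.

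On the laboratory day, a reader might infer that Day 14 cannot be shorthand for Day 15, because other SAP sections list both days. The documents do not support that. The eye, vital-sign and ECG assessments in those sections are scheduled on both days. SAP 12.8 also reports as Day 15 a COVID-19 test that protocol 8.3.2 allows on Day 14 or Day 15, so single-label usage does occur.

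**Conclusion.** The point holds as a gap between the endpoint definition and the SAP's analysis text. Followed as written, SAP 12.1.1 does not produce the primary safety estimate or its interval. This conclusion rests on the wording alone. The numerical illustration rests on assumed counts, and its upper values require little or no overlap between severe and serious participants.

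Two further inferences are not supported. One is that the SAP replaced or dropped the primary safety endpoint: SAP 5.1 and 6.4 retain it and SAP 8 declares no change. The other is that a trial conclusion would change: the protocol plans no formal comparison for this endpoint, and the requirement for acceptable safety carries no numerical limit, so no test or decision threshold moves. It should be fixed as a reporting correction.

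The laboratory day is a separate, minor correction. One of four post-baseline visits has no matching summary day. Whether its column would actually be missing depends on how the database labels that visit, which the documents do not show. A reader might infer that the end-of-treatment values would be lost, but SAP 12.7 lists all laboratory results.

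**What to change.** **SAP 12.1.1.** Make the primary table the n (%) of Safety-population participants with at least one severe (Grade 3 or higher) and/or serious AE from Day 1 through Day 15, by treatment group, with a mid-P 95% CI. Keep the 1, 2, ≥3 distributions for severe and for serious AEs as supportive tables. Cost: one derived participant-level flag and one row with a CI per group, using code already in Appendix 4. No new data are needed.

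**Laboratory label.** Replace Day 14 with Day 15 for the safety laboratory summaries and shift tables in SAP Tables 2 and 4 and section 12.7, and in protocol Tables 2, 6 and 9 and section 9.4.2.2. Some of these seven places name the day more than once. The sampling schedule does not change.

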12.1.2 Secondary Safety Analyses

12.1.2.1 Adverse Events

An AE overview table containing frequency and proportion (expressed in percent) of participants with AEs from Day 1 through Day 15 will be summarized by treatment group for the following:

- Any AE
- AEs with highest intensity [Grade 1, 2, and ≥ 3 (severe)]
- AEs related to study drug
- AEs leading to study drug discontinuation
- Serious AEs
- Serious adverse drug reactions
- AEs of special interest (AESI)

In this trial the following AEs will be reported as AESI:

- Anaphylactic reaction

- \geq Grade 2 intensity and/or serious AE related to increase of HR;
- \geq Grade 2 intensity and/or serious AE related to decrease of SBP;
- \geq Grade 2 intensity and/or serious AE related to decrease of DBP;
- \geq Grade 2 intensity and/or serious eye symptom-related AE;
- Per clinical discretion, the Investigator has clinical discretion to call an AE as an AESI even if these specific grading criteria are not specifically met.

Additionally, the frequency of AEs and frequency and proportion (expressed in percent) of participants with AE will be provided by SOC and PT and by treatment group for the following:

- Any AE
- AEs with highest intensity [Grade 1, 2, and ≥ 3 (severe)]
- AEs related to study drug
- AEs leading to study drug discontinuation
- Serious AEs

The frequency of AEs and frequency and proportion (expressed in percent) of participants with AE will be provided by PT and by treatment group for the following:

- Serious adverse drug reactions
- AEs of special interest

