6.3.2. Masking (Blinding)

This study will be open label for study participants, study site personnel, IDMC members, laboratory personnel involved in PK measurements and all sponsor and CRO personnel.

The study will instead be masked (blinded) for personnel involved in the conduct of all other laboratory procedures (including those for the primary endpoint).

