10.2.5. Definition of AESI

Adverse events of special interest (AESIs) are adverse events that the sponsor wants to monitor carefully and which are subject to expedited reporting (within 24 hours) from the investigator to the Sponsor or representative following the same process and timelines than the SAEs.

In this trial the following AEs will be collected and reported as AESI:

- Anaphylactic reaction
- \geq Grade 2 intensity (severity) and/or serious AE related to increase of heart rate (HR);
- \geq Grade 2 intensity (severity) and/or serious AE related to decrease of SBP;
- \geq Grade 2 intensity (severity) and/or serious AE related to decrease of DBP;
- \geq Grade 2 intensity (severity) and/or serious eye symptom-related AE.

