10.2.6.3. Assessment of AE/SAE Intensity

The investigator will assess intensity (severity) for each AE and SAE reported during the study and assign 1 of 5 grades:

- Grade 1: Mild
- Grade 2: Moderate
- Grade 3: Severe
- Grade 4: Potentially life-threatening
- Grade 5: Death (where applicable)

It is recommended that definitions provided in the Division of AIDS (DAIDS) Table for Grading the Severity of Adult and Pediatric Adverse Events, Version 2.1 of July 2017 (reported in Section 10.4, Appendix 4) be followed. The DAIDS Table provides definitions of intensity grades 1 to 4 for numerous major clinical conditions and laboratory parameters, organized by body system. Furthermore, for conditions and parameters not specifically identified, the DAIDS

It should be noted that the investigator is not obliged to use the definitions reported in Appendix 4 and medical judgement should prevail.

An event is defined as 'serious' when it meets at least 1 of the predefined outcomes as described in the definition of an SAE (see Section 10.2.2), **not** when it is rated as severe.

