8 CHANGES IN CONDUCT / RE-LANNED ANALYSES FROM THE PROTOCOL

No changes have been made to the planned analyses.

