9.6 Masking (Blinding)

This study will be open label for study participants, study site personnel, IDMC members, laboratory personnel involved in PK measurements and all sponsor and CRO personnel. The study will be masked (blinded) for personnel involved in the conduct of all other laboratory procedures (including those for the primary end-point).

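### The SAP adds investigator-nominated events to the protocol's closed AESI list and tabulates both together by regimen, so AESI proportions mix a set definition with unmasked labelling

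*SAP*

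**What the plan says.** **Protocol.** Section 10.2.5 introduces its list with "In this trial the following AEs will be collected and reported as AESI". Five items follow: anaphylactic reaction, then AEs of increased heart rate, decreased systolic pressure, decreased diastolic pressure and eye symptoms. The last four carry a threshold of at or above Grade 2 or seriousness; the eye item, for example, reads (after the at-or-above sign) "Grade 2 intensity (severity) and/or serious eye symptom-related AE". There is no discretion item. Sections 8.3.5, 8.3.6 and 8.3.7 also use a Grade 2 threshold and add none.

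**SAP.** Section 12.1.2.1 repeats the five items and adds a sixth: "the Investigator has clinical discretion to call an AE as an AESI even if these specific grading criteria are not specifically met". AESI is then one row of the Day 1 to Day 15 overview table and has its own table, for which "The frequency of AEs and frequency and proportion (expressed in percent) of participants with AE will be provided by PT and by treatment group". Neither output is split by the route through which an event became an AESI. Section 12.1 plans separate listings for serious AEs, AEs leading to discontinuation and deaths, but not for AESI. Appendix 5 of the SAP records the addition under Amendment 1 as a clarification of how AESI are determined.

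**Masking.** Protocol 6.3.2 states "This study will be open label for study participants, study site personnel, IDMC members". SAP 9.6 agrees; of masked staff it says "The study will be masked (blinded) for personnel involved in the conduct of all other laboratory procedures", meaning laboratory work other than PK. The person applying the discretion therefore knows the regimen.

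**The concern.** An AESI table by regimen is useful if the same rule decides membership in every group. Here membership can also follow from a decision by someone who knows the dose, with no written criterion and no record in the table of which events came in that way.

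Three features of the trial make this worth tidying:

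- Protocol 2.3 reports that the phase 1 heart-rate, blood-pressure and eye events were dose related and mostly mild. Mild is Grade 1, so the added route reaches a class of event that the protocol threshold keeps out unless it is serious.
- The protocol states an expectation about regimens: eye symptoms appeared linked to peak concentration, so splitting the daily dose might be better tolerated. That expectation could influence labelling.
- Under Protocol 6.3.1 only Cohorts II and III are randomized against each other. A labelling habit that changed over calendar time would coincide with dose.

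What is at stake is how the AESI rows read across regimens, in a trial meant to help choose dose regimens for later studies.

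**Working it through.** **1. Definitions side by side.**

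- Protocol 10.2.5: five items, four of them requiring Grade 2 or above and/or serious; no other route.
- SAP 12.1.2.1: the same five, plus events the investigator calls AESI although the grading criteria are not met.
- Difference: the SAP set contains the protocol set and can exceed it. It cannot lose a protocol-defined event.

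**2. Scope of the addition.** Two readings are possible. The broad one is any AE at all, because the clause refers simply to an AE. The narrow one is a waiver of the grade only, within the heart-rate, systolic, diastolic and eye items, because the clause refers to these grading criteria and follows the graded items. The text does not settle which. Mild eye and heart-rate events are covered under both.

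**3. Plan's own figures.** Neither document states an AESI rate, so there is none to reproduce. As a check on the group size, the safety probabilities in SAP 6.2 follow from 1 − (1 − p)^n:

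- n = 15, p = 10%: 79.4% (stated about 80%)
- n = 15, p = 15%: 91.3% (stated 90%)
- n = 15, p = 5%: 53.7% (stated 54%)
- n = 75, p = 3%: 89.8% (stated 90%)

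These agree with the plan and confirm N = 15 as the working denominator.

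**4. Weight of one label.** 1/15 = 6.7 percentage points per participant added.

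**5. Illustration (assumed rates).** Let g2 be the share of participants meeting the protocol criteria, g1 the share with only a below-threshold event, and q the share of the latter labelled AESI. The expected tabulated proportion is g2 + q × g1. With g2 = 10% and g1 = 20%:

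- q = 0: 10% (1.5 of 15)
- q = 0.25: 10 + 5 = 15% (2.25 of 15)
- q = 0.5: 10 + 10 = 20% (3 of 15)
- q = 1: 10 + 20 = 30% (4.5 of 15)

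Two regimens with the same true event rates, one labelled at q = 0 and the other at q = 0.5, would be expected to show 10% and 20%. For g1 from 10% to 40%, labelling half adds 0.5 × 10 = 5 to 0.5 × 40 = 20 points, whatever g2 is. None of g1, g2 or q comes from the documents.

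**6. Noise at this size.** Exact (Clopper-Pearson) 95% intervals are 0 to 21.8% for 0/15 and 4.3 to 48.1% for 3/15. They overlap, so a three-participant labelling difference would alter the impression the table gives without being firm evidence of anything.

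**The case against.** The strongest reply is that little depends on this table.

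- AESI appears in no objective or endpoint table of the protocol, nor in its summary of analyses (Table 9) or its safety-analysis section (9.4.2). In the protocol it is an expedited-reporting category.
- The primary safety endpoint is Grade 3 or above and/or serious. The pausing rules in Protocol 7.1 and the IDMC review in 9.7.1 do not use an AESI count.
- The same events are reported by regimen without the label: eye-symptom AEs of all grades (SAP 12.2), heart rate and blood pressure against 25% thresholds (12.5), ECG heart rate (12.6), and AEs by highest grade (12.1.2.1). If two cohorts had the same Grade 1 eye events and only one cohort's were labelled, the section 12.2 tables would match and expose the labelling.
- The protocol definition is not free of judgement either. The same investigator grades the event, and Protocol 10.2.6.3 says the "investigator is not obliged to use the definitions reported in Appendix 4 and medical judgement should prevail".
- Nothing in the documents shows that discretion would be used often, or differently by dose.

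All of this stands, and it limits the importance of the point. It does not make the AESI rows interpretable as they are. A recorded grade can be seen and tabulated; a discretionary AESI label, as planned, cannot be told apart from a criterion-based one.

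**Conclusion.** The point holds as a minor one. The SAP widens a closed list, and its by-regimen AESI outputs do not separate protocol-defined from investigator-nominated events. The size is 6.7 points per participant added, at the planned 15 per group; any total effect depends on assumed labelling rates. The primary safety endpoint is unaffected.

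Three stronger readings are tempting but not supported:

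- A reader might infer that SAP section 8, which says "No changes have been made to the planned analyses", is false. The protocol plans no AESI analysis, so widening the definition changes no analysis it planned. The addition is also disclosed in the SAP history.
- A reader might infer that any AE whatever can become an AESI. That is one reading; the narrower one, waiving only the grade within the listed categories, fits the words as well.
- A reader might infer that a dose trend in AESI would be an artefact of labelling. The documents show that this could happen, not that it would. The phase 1 events show what could be labelled, not how often it would be done.

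**What to change.** - Derive a protocol-defined AESI flag by program from the coded term, recorded grade and seriousness, following Protocol 10.2.5, and use it for the overview row and the table by preferred term. Fix the list of terms for each category before database lock.
- Show investigator-nominated AESI that do not meet that definition in a separate row of both tables.
- State in SAP 12.1.2.1 whether the discretion covers any AE or only lower-grade events in the listed categories.
- When programming the eye item, note that Protocol 8.3.7 pairs the Grade 2 threshold with severe where 10.2.5 has serious. The two should be reconciled; the flag above follows 10.2.5.

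The cost is one derived variable, one extra row in two tables and a sentence or two of text. No new data are needed, and investigators keep their discretion to nominate events, so expedited reporting is unchanged. The change removes one layer of unmasked judgement, not all of it, because the grade feeding the flag is still assigned by the investigator.
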